6.1.14 Efficacy Evaluation

Efficacy evaluation of AML will be performed based on 2017 European LeukemiaNet (ELN) criteria ([Appendix 8](#)). Efficacy evaluation of HR-MDS will be performed based on the International Working Group response criteria in myelodysplasia ([Appendix 12](#)). Efficacy evaluation of AITL will be performed based on Lugano Classification ([Cheson 2014](#)) for Hodgkin and Non-Hodgkin's Lymphoma ([Appendix 9](#)).

Tumor evaluations will be conducted at screening, every 8 weeks (± 7 days) during the first 24 weeks (ie, Day 1 of Cycles 3, 5, and 7), and every 12 weeks (± 14 days) thereafter (ie, Day 1 of Cycles 10, 13, and so on) through EOT, or end of Efficacy Follow-up period (if applicable). Patients who discontinue HMPL-306 treatment due to reasons other than disease progression will continue tumor assessment according to previous tumor evaluation schedule until disease progression, as defined in [Appendix 8](#) and [Appendix 9](#), or start of new antineoplastic therapy (see [Table 1](#)). The same imaging procedure and laboratory tests used to define measurable lesions at baseline should be used throughout the study for each patient.

The baseline tumor assessment should be completed within 28 days prior to the first dose of study treatment (depending on the patient's disease status, a window may be acceptable based on a discussion between the investigator and the sponsor's medical monitor). Tumor assessments completed as standard of care, prior to signing of the informed consent and within 28 days of first dose of study treatment, may be used as baseline assessment.

Response evaluation of patients will be based on the most recent results of physical, bone marrow (if applicable), imaging, and hematological examinations, per local assessment. If a patient needs to delay the study drug after bone marrow examination and wait for recovery of peripheral blood count, then routine blood test results within 2 weeks after bone marrow analysis can be used to determine response.

For patients with myeloid malignancies, this assessment should be done using a blood test, bone marrow aspiration and/or biopsy, and physical examination as per the Schedule of Events (see [Table 1](#)).

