6.1.19 Follow-up Period

Safety Follow-up

All patients who have completed an EOT Visit will have a Safety Follow-up Visit. The Safety Follow-up Visit will be conducted at 30 days (± 7 days) from EOT Visit.

AEs related to the study drug will be followed until resolution and SAEs will be followed until resolution regardless of the relationship to the study drug.

All female patients of childbearing potential must complete a pregnancy test (serum or urine) during the Safety Follow-up Visit. Pregnancy testing should be repeated for patients with suspected pregnancy. This is not applicable for postmenopausal female patients (defined as at least 12 months of amenorrhea without alternative medical cause), and the date of menopause should be recorded instead.

Efficacy Follow-up

Patients who discontinue the study drug due to reasons other than disease progression, death, lost to follow-up, or withdrawal of consent will remain on study for tumor assessments and will be followed every 12 weeks (± 14 days) from the EOT visit or last assessment, until disease progression, initiation of new anticancer therapy, withdrawal of consent, lost to follow-up, death, conditions are met per Section [6.2.1](#), or the end of the study, whichever comes first.

Survival Follow-up

All patients will be followed for survival status every 12 weeks (± 14 days), until death, lost to follow-up, or withdrawal of consent. Survival information can be obtained via phone and information will be documented in the source documents and relevant CRFs.

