- Primary refractory AML unsuitable for intensive chemotherapy or venetoclax-based regimen or target agents;
- Relapsed/refractory AML that has progressed on prior IDH treatment

The sponsor, in consultation with SRC, may decide to increase or decrease the number of enrolled patients in each cohort, depending on preliminary clinical response, safety signals, or operational feasibility. Patients who are not efficacy evaluable in any cohort may be replaced.

The overall study schema is presented in [Figure 1](#).

Figure 1 Study Schema

Any patient who discontinues treatment should be encouraged to return to the study site for an End of Treatment (EOT) Visit and continue with the remaining study visits. Patients must be discontinued from treatment for disease progression, withdrawal of consent, intolerable toxicity, repeated non-compliance or poor compliance, commencement of other antitumor treatment during the study, pregnancy, loss to follow-up, termination of the study by the sponsor, death, or end of the study.

Patients who discontinue the study drug due to reasons other than disease progression, death, lost to follow-up, or withdrawal of consent will remain on study for tumor assessments and will be followed every 12 weeks (± 14 days) from the EOT visit or last assessment, until disease progression, initiation of new anticancer therapy, withdrawal of consent, lost to follow-up, death, conditions are met, or the end of the study, whichever comes first. Survival information can be obtained via phone and information will be documented in the source documents and relevant case report forms (CRFs). The end of study is defined as the date on which all patients have their last visit or 1 year after the last patient has their first visit, whichever comes first.

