4.2.3. Duration of Response

Some duration (months) of responses are defined as follows:

- Duration of CR (DOCR) is defined as the time from the first occurrence of CR until disease progression, relapse, or death due to any cause, whichever comes first. Only patients with CR will be included in this analysis.
- Duration of CRh (DOCRh) is defined as the time from the first occurrence of CRh until disease progression, relapse, or death due to any cause, whichever comes first. Only patients with CRh will be included in this analysis.
- Duration of cCR-1 (DOcCR1) is defined as the time from the first occurrence of cCR-1 until disease progression, relapse, or death due to any cause, whichever comes first. Only patients with cCR-1 will be included in this analysis.
- Duration of cCR-2 (DOcCR2) is defined as the time from the first occurrence of cCR-2 until disease progression, relapse, or death due to any cause, whichever comes first. Only patients with cCR-2 will be included in this analysis.
- Duration of cCR-3 (DOcCR3) is defined as the time from the first occurrence of cCR-3 until disease progression, relapse, or death due to any cause, whichever comes first. Only patients with cCR-3 will be included in this analysis.
- Duration of objective response (DOOR) is defined as the time from the first occurrence of objective response (CR_{MRD}-, CR, CRh, CRi, MLFS, or PR) until disease progression, relapse, or death due to any cause, whichever comes first. Only patients with objective response will be included in this analysis.

The duration (months) of response is generally calculated as (date of death or PD or Relapse or last assessment – date of first occurrence of interested response category + 1)/30.4375. The rule of censoring will follow these rules outlined in [Table 2](#).

Table 2 Outcome and Event or Censoring Dates for Duration of Response

Rule	Situation	Date of Event or Censoring	Outcome
1	Relapse (or PD) documented between schedule tumor assessment visits or after one missing tumor assessment visit	Date of first documented relapse (or PD)	Event
2	Death without relapse (or PD) between scheduled assessment visit or death after one missing tumor assessment visit	Date of death	Event

4	No death or relapse (or PD) by the time of data cut-off for final analysis	Date of last adequate tumor assessment prior to or on analysis data cutoff date	Censored

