5	Early discontinuation (lost to follow-up or withdrawal of consent) of study without death or relapse (or PD)	Date of last adequate tumor assessment	Censored
6	Subsequent anti-tumor therapy started prior to relapse (or PD) or death	Date of last adequate assessment prior to or on date of initiation of subsequent anti-tumor therapy	Censored
7	Death or relapse (or PD) after two or more consecutive missed or inadequate tumor assessment visits	Date of last adequate tumor assessment prior to missed visits	Censored

PD is only applicable for the duration of objective response.

Note: An adequate tumor assessment is defined as an assessment where the Investigator determined response is CR_{MRD}-, CR, CRh, CRI, MLFS, PR, SD, and PD. If PD and subsequent anti-cancer therapy occur on the same day, will assume that the progression was documented first, e.g. outcome is progression and the date is the date of the assessment of progression.

(a) Determination of one missing or inadequate assessment

The following provides the rules for determining whether one tumor assessments is missed, of note, the relative day in the rules refers to the first dose date of study drug from Cycle 1 in continuous cycle.

- If the tumor assessment date is prior to day 1 of week 23 (relative day $< (24 - 1) \times 7 + 1 = 162$), and the difference between the tumor assessment date and the next adjacent adequate tumor assessment ≥ 63 days (8 weeks * 7 + 7), then the tumor assessment is considered as occurring after one missing tumor assessment;
- If the tumor assessment date is on or after day 1 of week 23 (relative day $< (24 - 1) \times 7 + 1 = 162$), and the difference between the tumor assessment date and the next adjacent adequate tumor assessment ≥ 98 days (12 weeks * 7 + 14), then the tumor assessment is considered as occurring after one missing tumor assessment.

(b) Determination of two or more consecutive missing or inadequate assessments

The following provides the rules for determining whether two or more consecutive tumor assessments are missed.

- If the tumor assessment date is prior to day 1 of week 15 (relative day $< (16 - 1) \times 7 + 1 = 106$), and the difference between the tumor assessment date and the next adjacent adequate tumor assessment ≥ 126 days ($= 2 * (8 \text{ weeks} * 7 + 7)$), then the tumor assessment is considered as occurring after two or more consecutive missing tumor assessments;

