- If the tumor assessment date is between day 1 of week 15 and day 1 of week 23 (relative day between $(16 - 1) \times 7 + 1 = 106$ and $(24 - 1) \times 7 + 1 = 162$), and the difference between the tumor assessment date and the next adjacent adequate tumor assessment ≥ 161 days ($= (8 \text{ weeks} * 7 + 7) + 12 \text{ weeks} * 7 + 2 \text{ weeks} * 7$)), then the tumor assessment is considered as occurring after two or more consecutive missing tumor assessments;

- If the tumor assessment date is on or after day 1 of week 23 (relative day $\geq (24 - 1) \times 7 + 1 = 162$), and the difference between the tumor assessment date and the next adjacent adequate tumor assessment ≥ 196 days ($= 2 * (12 \text{ weeks} * 7 + 2 \text{ weeks} * 7)$), then the tumor assessment is considered as occurring after two or more consecutive missing tumor assessments.

Reasons for censoring are included in Table 3 following the hierarchy.

Table 3 Duration of Response Censoring Reasons and Hierarchy

Hierarchy	Condition	Censoring Reason
1	Subsequent anti-tumor therapy started prior to relapse (or PD) or death	Subsequent anti-tumor therapy started prior to relapse (or PD) or death
2	Death or relapse (or PD) after two or more consecutive missed or inadequate tumor assessment visits	Missed or inadequate two or more consecutive tumor assessment visits
3	Drops out before end of study, no relapse (or PD) or death, lost to follow-up	No death or relapse (or PD), lost to follow-up
4	Drops out before end of study no relapse (or PD) or death, withdrawal by subject from the study	No death or relapse (or PD), withdrawal by subject
5	No death or relapse (or PD) by the time of data cut-off for the analysis	No death or relapse (or PD) by the time of data cut-off for the analysis

PD is only applicable for the duration of objective response.

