6	CR by 24 weeks ^a then start subsequent anticancer therapy (prior to death or relapse or no relapse)	Date of the last adequate disease assessment documenting no relapse prior to start of subsequent anticancer therapy or missed response assessments	Censored
7	CR by 24 weeks ^a then death or relapse after missed or inadequate two or more consecutive tumor assessments		Censored
8	CR by 24 weeks ^a and neither relapse nor death		Censored
9	No baseline or post-baseline adequate disease assessment	Date of first administration of study treatment	Censored

CR: including CRMRD-, CR, CRh and CRi; EFS = event-free survival; TF = treatment failure.

^aBased on the protocol schedule of assessments, “+1 week window” is allowed.

Note: The same algorithm for determination of one and two/more consecutive missing or inadequate assessments can be found in [Section 4.2.3..](#)

Reasons for censoring are included in [Table 5](#) following the hierarchy.

Table 5 EFS Censoring Reasons and Hierarchy

Hierarchy	Condition	Censoring Reason
1	No baseline or post-baseline adequate disease assessment	No baseline or post-baseline tumor assessments
2	On treatment $<$ 24 weeks without CR and active in study	On treatment $<$ 24 weeks, active in study
3	CR by 24 weeks then start subsequent anticancer therapy	CR by 24 weeks, start subsequent anticancer therapy
4	CR by 24 weeks then death or relapse after missed or inadequate two or more consecutive tumor assessments	CR by 24 weeks, missed or inadequate two or more consecutive tumor assessments
5	CR by 24 weeks, no relapse or death, lost to follow-up	CR by 24 weeks, lost to follow-up

6	CR by 24 weeks, no relapse or death, withdrawal by subject from the study	CR by 24 weeks, withdrawal by subject
7	CR by 24 weeks, no relapse or death, ongoing in study	CR by 24 weeks, ongoing without relapse or death

CR: including CRMRD-, CR, CRh and CRi; EFS = event-free survival.

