4.2.7. Progression-free Survival

Progression-free Survival (PFS) is defined as the time (months) from the start of study treatment from Cycle 1 in continuous cycle (i.e. not from the date of single oral dose from the PK week for the dose escalation part) to disease progression, or relapse, or death due to any cause, whichever occurs first. More specifically, PFS will be determined using all the assessment data up until the last evaluable visit prior to or on the date of

- (i) disease progression (at least 2 cycles of study drug should be administered to determine PD) or relapse as defined by 2017 ELN criteria for AML patients, or
- (ii) withdrawal of consent; or lost to follow-up, or
- (iii) receiving subsequent anti-tumor therapy, whichever is earlier.

Patients without report of PD or death due to any cause at the time of analysis are censored as described in [Table 7](#) below.

Table 7 Outcome and Event or Censoring Dates for PFS

Rule	Situation	Date of Progression or Censoring	Outcome
------	-----------	----------------------------------	---------

1	PD/relapse documented between schedule tumor assessment visit or after one missing tumor assessment visit	Date of first documented disease progression/relapse	Event
2	Death without PD/relapse between schedule tumor assessment visit or death on or before the second scheduled visit or death after one missing tumor assessment visit	Date of death	Event
3	No baseline or post-baseline tumor assessments available and subject dose not die	Date of first administration of study treatment	Censored
4	No death or PD/relapse by the time of data cut-off for final analysis	Date of last adequate tumor assessment prior to or on analysis data cutoff date	Censored
5	Early discontinuation (lost to follow-up or withdrawal of consent) of study without death or PD/relapse	Date of last adequate tumor assessment	Censored
6	Subsequent anti-tumor therapy started prior to PD/relapse or death	Date of last adequate assessment prior to or on date of initiation of subsequent therapy visit	Censored
7	PD/relapse or death after missed or inadequate two or more consecutive tumor assessment visits	Date of last adequate tumor assessment prior to missed visits or date of first administration of study treatment (if no post-baseline tumor assessment)	Censored

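### For patients assessed at EOT before Day 162 and then followed 12-weekly, SAP 4.2.3(b) can censor PD found after one missed visit as if two had been missed

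*SAP*

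**What the plan says.** **The limits.** SAP Section 4.2.3(b) has three tiers, set by days since the first continuous dose, with no distinction between patients on and off drug:

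- "If the tumor assessment date is prior to day 1 of week 15" (given as before Day 106): a gap of 126 days or more means two or more missed assessments.
- "If the tumor assessment date is between day 1 of week 15 and day 1 of week 23" (given as Days 106 to 162): 161 days or more.
- From Day 162: 196 days or more.

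**What the limits decide.** Rule 1 of SAP Table 2 makes this an event: "Relapse (or PD) documented between schedule tumor assessment visits or after one missing tumor assessment visit". Rule 7 of that table censors at the last adequate assessment once two or more have been missed. Table 7 (PFS) has the same pair, with rule 7 worded "PD/relapse or death after missed or inadequate two or more consecutive tumor assessment visits". In Table 4 (EFS), rule 7 applies to patients with CR by 24 weeks, "then death or relapse after missed or inadequate two or more consecutive tumor assessments". PFS and EFS both take the missed-visit algorithm from Section 4.2.3.

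**The off-drug schedule.** Under protocol Section 6.1.19, patients who stop drug for reasons other than progression "will remain on study for tumor assessments and will be followed every 12 weeks" (±14 days). SAP Section 2.2 repeats this and counts "from the EOT visit or last assessment, until disease progression, initiation of new anticancer therapy". The Efficacy Follow-up column of protocol Tables 1 and 2 agrees. Protocol Section 6.1.14 does not: there the same patients "will continue tumor assessment according to previous tumor evaluation schedule until disease progression". Tables 1 and 2 also schedule a tumor evaluation at EOT, and Section 6.1.10.3 schedules marrow there.

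**The concern.** The limits are built from 8-weekly visits to week 24 and 12-weekly visits after that. A patient who stops drug early moves to 12-weekly visits at once, but the algorithm still applies the shorter limits because it looks only at study day. One missed 12-weekly visit can then exceed a limit meant for two missed visits. The same observation is an event under rule 1 and censored under rule 7, and the computed gap decides in favour of censoring. PFS and duration of response could each lose a documented event. EFS could too, but only in patients with CR, CRMRD-, CRh or CRi by week 24; others who stop early are already events at Day 1 under rule 4 of Table 4.

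**Working it through.** **1. Reproduce the SAP's figures.**

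- Limits: 2 × (8×7 + 7) = 126; (8×7 + 7) + (12×7 + 14) = 161; 2 × (12×7 + 14) = 196.
- Cut-offs: (16 − 1)×7 + 1 = 106; (24 − 1)×7 + 1 = 162. These are the first days of the C5D1 window (113 − 7) and the C7D1 window (169 − 7). They are day 1 of weeks 16 and 24, not 15 and 23 as labelled; I use the day numbers.

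**2. Which assessment sets the limit.** The SAP does not say. If it were the later one (the PD), a PD by Day 105 lies at most 105 − 1 = 104 days after Day 1, below 126. A PD by Day 161 lies at most 161 − 1 = 160 days after, below 161. The first two limits could then be reached only against a baseline assessment. Also, 63 + 98 = 161 describes a last adequate assessment around C5D1 followed by an 8-week and then a 12-week interval. So the earlier, last adequate assessment must set the limit.

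**3. On treatment the limits work.** Nominal visits are Days 57, 113, 169, 253, 337 and 421.

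| Last adequate | Limit | Gap, one missed | Gap, two missed |
|---|---|---|---|
| Day 57 | 126 | 112 | 196 |
| Day 113 | 161 | 140 | 224 |
| Day 169 | 196 | 168 | 252 |

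No one-missed gap reaches its limit and every two-missed gap does.

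**4. Off drug, 12-weekly, adequate assessment at EOT, one visit missed.** The gap is 2 × 84 = 168 days, or 154 to 182 with the ±14-day window (29 possible days).

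| EOT assessment | Limit | Days classed as two missed |
|---|---|---|
| Before Day 106 | 126 | 29 of 29 |
| Days 106–161 | 161 | 22 of 29 (gaps 161–182), 76% |
| Day 162 or later | 196 | 0 of 29 |

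If the last adequate assessment is itself a 12-weekly follow-up visit, both visits have windows. The gap is then 140 to 196 days over 29 × 29 = 841 pairs. The counts are 841 of 841, 610 of 841 (73%) and 1 of 841. The percentages treat all window days as equally likely.

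**5. Off drug under protocol Section 6.1.14 instead.** From Day 57 the one-missed gap is 112 ± 14 days and reaches 126 in 1 of 225 window pairs. From Day 113 it is 140 ± 21 days and reaches 161 in 1 of 435. The problem essentially disappears.

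**6. Example.** There is an adequate EOT assessment on Day 57, the Day 141 visit (57 + 84) is missed, and PD is found on Day 225 (57 + 168). The gap is 168 ≥ 126, so rule 7 applies. PFS is censored at 57/30.4375 = 1.9 months. Rule 1 would give an event at 225/30.4375 = 7.4 months.

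**The case against.** **The wording can be read the other way.** Each tier begins with the tumor assessment and ends by saying that this assessment comes after the missed ones. Grammatically that points to the later assessment. On that reading the Day 225 PD falls under the 196-day limit and stays an event. The ambiguity is real, and the point rests on an inference. But the later-assessment reading leaves two of the three tiers with almost no use (step 2), so it is unlikely to be what was meant.

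**The schedule is disputed.** If protocol Section 6.1.14 governs, the existing limits are adequate. That stands. However, Section 6.1.19, both schedule tables and SAP Section 2.2 say 12-weekly, and no document says which prevails.

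**A missed EOT assessment changes the answer.** A reader might infer that any off-drug PD after one missed follow-up visit is wrongly censored, even when the last adequate assessment was an earlier on-treatment visit. The documents do not support this. A tumor evaluation is due at EOT. If it was missed or inadequate and the next visit was missed too, two consecutive assessments are missing and censoring is what rule 7 intends. This also rules out a blanket 196-day limit. Suppose the last adequate assessment is Day 57, EOT on Day 77 has no adequate assessment, the Day 161 visit is missed and PD is on Day 245. The gap is 245 − 57 = 188 days. A 196-day rule would count an event despite two missed assessments.

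**Few patients qualify and little depends on them.** A patient must stop before Day 162 without PD, start no new therapy, miss exactly one visit, then return with PD or relapse. SAP Table 13 notes that Part 2 enrolled one patient; Part 1 was planned at 24 to 30 evaluable. The endpoints are secondary with no hypothesis test, and all efficacy data are listed. All of this stands and sets the severity.

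**Conclusion.** The point holds, and it is minor. For patients with an adequate EOT assessment before Day 162 who are then followed 12-weekly, SAP Section 4.2.3(b) contradicts rule 1 of Tables 2 and 7. PD or relapse after one missed visit is censored always if that assessment is before Day 106, and on 22 of 29 window days if it is on Days 106 to 161.

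This rests on two assumptions: the last adequate assessment sets the limit, and the 12-weekly schedule of Section 6.1.19 applies.

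Essentially unaffected are:

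- patients whose last adequate assessment is on or after Day 162. This includes most who stop at the 6-cycle cap: last dose is about Day 168 (6 × 28) and C7D1 falls on Days 162 to 176;
- patients actually followed 8-weekly;
- patients censored for subsequent therapy.

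The window fractions say how the rule behaves once a visit is missed, not how often that happens. The number affected is unknown and probably very small. Nor do the documents support a claim that median PFS is biased in a known direction: that depends on where the lost event falls among the others. One lost event could still matter in a dose level of about three patients, because efficacy is summarised by dose level.

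**What to change.** Amend SAP Section 4.2.3(b) before database lock:

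1. For off-drug patients on 12-weekly follow-up, count missed scheduled assessments, including a missed or inadequate EOT assessment. Apply rule 7 only when two or more consecutive ones are missed. Equivalently, use a limit of more than 196 days regardless of study day, but only when the last adequate assessment is the EOT assessment or a preceding 12-weekly follow-up assessment. With that limit no one-missed gap is flagged (the maximum is 196) and every two-missed gap is (224 to 280 days).
2. Keep the existing limits for on-treatment intervals and for patients actually followed 8-weekly. For the latter, two missed visits give 168 ± 14 = 154 to 182 days, which a 196-day limit would never catch.
3. State that the earlier (last adequate) assessment sets the limit.
4. State whether protocol Section 6.1.14 or 6.1.19 governs off-drug assessments.

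The cost is one added condition and a few clarifying sentences, with the matching programming change. No new data are needed.
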